2. De novo (new affirmative response of > 1 to Question 16 on PFDI-20) or worsening urge incontinence symptoms (increase of score on Question 16 by 2 points or more on PFDI-20) at 12 months post-operatively.
3. Surgeon satisfaction with the sling will be assessed immediately post-operatively with a 10-point VAS.
4. Patient Global Impression of Improvement (PGI-I) Scale for incontinence symptoms.²⁶
5. Need for bladder drainage beyond 6 weeks post-operatively

POWER CALCULATION:

This study is a non-inferiority study design. The null hypothesis is that the difference in the proportion of women with abnormal bladder function in the SIS group compared to RP sling group is 12% or more (noninferiority margin: H0: RP-SIS_ 0.12). Based on criteria used in a previously published multicenter trial of mid-urethral slings, we chose a noninferiority margin of 12%. Assuming a subjective cure rate for RP of 82%, 127 individuals in each group will provide 80% to reject the null hypothesis (H0) that the true difference in cure rates between the two procedures (% cure RP and % cure ALTIS SIS sling) is less than or equal to 12% in favor of the alternate hypothesis (H1: SIS-RP_ 0.12) that the true difference

in proportions is greater than 12% using a two-group large-sample normal approximation test of proportions with a one-sided 5% significance level. Assuming a 10% loss to follow-up or drop-out rate for the duration of the study, the total enrollment goal is 280. Non-inferiority was declared if the upper bound of the 95% confidence interval for the between group difference in bladder function was less than 12%. To minimize bias toward non-inferiority, only women treated per protocol (ie: underwent the randomized sling) were considered in the primary outcome analysis. A secondary analysis of the primary outcome was performed on the intent to treat population. Likewise, other secondary outcome measures were performed on the intent to treat population.

CALENDAR OF EVENTS

| | Baseline | Surgery | Day of DC | 2 weeks | 6 weeks | 6 months | 12 months |
|-------------------------------------|----------|---------|-----------|---------|---------|----------|-----------|
| Informed Consent | X | | | | | | |
| CRF | X | X | X | X | X | | X |
| Demographic information | X | | | | | | |
| Charlson Comorbidity Index | X | | | | | | |
| POP-Q | X | | | | X | | X |
| PFDI-20 short form | X | | | | X | | X |
| PFIQ -7 short form | X | | | | | | X |
| PISQ-IR | X | | | | | | X |

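### The trial is sized on a one-sided 5% test but non-inferiority is judged on a 95% confidence interval; read as two-sided, that rule has about 70% power, not the stated 80%.

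*Protocol*

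**What the plan says.** Both statements stand in one paragraph of the protocol, under Power Calculation.

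- **Sizing.** The assumptions are "Assuming a subjective cure rate for RP of 82" percent and "we chose a noninferiority margin of 12" percent. The protocol then says that "127 individuals in each group will provide 80% to reject the null hypothesis", with the test described as a "two-group large-sample normal approximation test of proportions with a one-sided 5% significance level". No cure rate is given for the SIS arm.
- **Success rule.** "Non-inferiority was declared if the upper bound of the 95% confidence interval for the between group difference in bladder function was less than 12" percent.

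The paragraph does not say whether the interval is one-sided or two-sided, and it mentions no 90% interval. The analysis it applies to is the per-protocol comparison of the primary composite outcome, abnormal lower urinary tract function at 12 months.

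**The concern.** A one-sided 5% test of non-inferiority is the same as asking whether the upper limit of a two-sided 90% interval (equivalently, a one-sided 95% upper bound) lies below the margin. Asking the same of a two-sided 95% interval is a one-sided 2.5% test. On the usual meaning of a 95% confidence interval, the trial was therefore sized with one critical value (1.645) and is judged with another (1.960).

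Two things follow. The stated power does not belong to the rule that decides the trial. And there is a band of results that are non-inferior by one sentence and not by the other. A reader of the protocol cannot tell which verdict binds, so the choice could be made or disputed once the data are known.

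**Working it through.** **Inputs** (Protocol, Power Calculation)

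- RP cure 82%, that is 18% failure; the variance is the same either way.
- Margin 0.12, absolute.
- 127 per group, power 80%, one-sided 5%.
- SIS cure is not stated. I assume 82%, a true difference of zero, and vary it below.

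**Step 1. Reproduce the protocol's sample size.** With the unpooled normal approximation,

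n per group = (z_alpha + z_power)² × 2 × 0.18 × 0.82 / 0.12²

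- One-sided 5%: (1.645 + 0.842)² × 0.2952 / 0.0144 = 126.7, so **127**. This matches the protocol and supports the equal-rates assumption.
- One-sided 2.5%: (1.960 + 0.842)² × 0.2952 / 0.0144 = 160.9, so **161**. This does not match.

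**Step 2. Power at 127 per group.** The standard error is √(0.2952 / 127) = 0.0482, and 0.12 / 0.0482 = 2.489. Power is Φ(2.489 − z_alpha).

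| Rule | z | Power, formula | Power, exact binomial enumeration of the Wald limit | Power, Farrington-Manning |
|---|---|---|---|---|
| One-sided 5% (two-sided 90% CI) | 1.645 | 80.1% | 80.2% | 79.2% |
| Upper limit of two-sided 95% CI | 1.960 | 70.2% | 70.4% | 68.9% |

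The gap of about 10 points does not depend on the method. Enrolling 280 and losing 10% leaves 280 × 0.9 / 2 = 126 per group, with power of 79.8% and 69.8%.

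**Step 3. Dependence on the unstated SIS rate.** RP cure is held at 82%, n = 127, and power is Φ((0.12 − d)/SE − z), where d is RP cure minus SIS cure and SE = √((0.82 × 0.18 + p(1 − p)) / 127) for SIS cure p.

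| SIS cure | SE | Power, one-sided 5% | Power, two-sided 95% CI |
|---|---|---|---|
| 80% | 0.0492 | 65.1% | 52.9% |
| 82% | 0.0482 | 80.1% | 70.2% |
| 84% | 0.0471 | 90.8% | 84.4% |

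The level moves a good deal with the assumption. The two-sided 95% rule has the lower power in every row.

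**Step 4. Where the two rules disagree.** Take the difference as SIS minus RP in the proportion with abnormal function. With the standard error held at 0.0482, the largest observed excess that passes is:

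- 0.12 − 1.645 × 0.0482 = 0.041, about 4.1 points, at one-sided 5%;
- 0.12 − 1.960 × 0.0482 = 0.026, about 2.6 points, under the two-sided 95% interval.

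If RP is fixed at 18% and the SIS variance grows with the excess, the limits are about 3.8 and 2.3 points. If the slings are truly equal, the result falls between the two limits about 10% of the time (80.1% − 70.2%).

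**The case against.** The strongest reply is that the protocol never calls the interval two-sided. It fixes a one-sided 5% level and refers only to the upper bound. A one-sided 95% upper bound is the exact counterpart of that test; on that reading the paragraph is consistent and the power stays at 80%. This may well be what was meant, so the 70% is conditional on the two-sided reading. But the text does not say one-sided, and the unqualified term is ordinarily read the other way. A statistical analysis plan, not seen here, may specify the interval, but that would not remove the ambiguity from the protocol's own success rule.

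Second, on the two-sided reading the rule is stricter than the test used for sizing. The one-sided error falls from 5% to 2.5%, so the risk is a non-inferior sling failing to be shown as such, not a false claim. This stands. It limits the harm but does not make the stated power correct.

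Third, equal cure rates are an inference, and 82% is a subjective cure rate, whereas the primary outcome also counts retreatment for stress incontinence and surgery for retention. Both points are fair. The 70% is the protocol's own planning calculation under the other alpha, not a forecast for the composite outcome.

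**Conclusion.** The concern holds. The sample size comes from a one-sided 5% test, and the success rule, read in the ordinary way, is a one-sided 2.5% test. On the protocol's figures, with SIS cure assumed equal to RP cure at 82%, power under that rule is about 70% instead of 80%. The chance of missing a truly equivalent sling rises from about 20% to about 30%. If a one-sided 95% bound was intended, 80% stands and only the wording is at fault. Because the conflict sits in the success criterion for the primary outcome, it must be resolved before the result can be read without dispute.

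**What to change.** Use one alpha throughout the Power Calculation section. There are two ways.

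- **(a) Keep the two-sided 95% interval.** Say that it is two-sided, restate the level as one-sided 2.5%, and give the power as about 70% with 127 per group. This can be done at any time because it does not loosen the success rule. The cost is a less favourable stated power. Keeping 80% under this rule would mean 161 per group, or 161 / 0.9 = 178.9, so 179 per group and 358 in total after 10% loss.
- **(b) Name the one-sided bound.** State that non-inferiority requires the upper limit of the two-sided 90% interval (one-sided 95% upper bound) to be below 12 points. This agrees with the sizing test and keeps 80% power with 127 per group. The cost is that the less strict 5% one-sided error becomes explicit. It is acceptable only if it was the intention from the start or is fixed before anyone has seen outcome data. The rule is written in the past tense, so the date and reason for the change should be recorded.

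Either is a change of a sentence or two and needs no additional patients. In both cases, state the SIS cure rate assumed in the calculation.

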NOTE: Standard of care assessments (POP-Q, UDS, PVRs) are valid to use for the study if they were performed within 6 months of the subject signing consent. Also, if any standard of care questionnaires (matching the study questionnaires) were administered within 6 months before signing consent, they may also be used

in the place of baseline questionnaires and not repeated. Dates of assessments just need to be clear if they were not performed the same day as baseline. Also, make sure all assessments required for the study have been performed per baseline visit requirements.

RANDOMIZATION AND MASKING:

A computer-generated random allocation using a randomly permuted block design (10 subjects per block) will be stratified by clinical site and presence of symptomatic versus occult SUI. Randomization will be assigned in the operating room to minimize surgeon and participant bias. While it is impossible for surgeons to be masked to the randomization, participants will be masked during the one-year follow-up period. Dictated operative notes will list the type of sling under procedures as “per study protocol” and then describe the type of sling used within the body of the operative note. Precautions will be taken to minimize unmasking the study groups: Since RP slings require two suprapubic stab incisions, identical sham incision will also be performed in the SIS group. Surgical wound dressings will be identical for all participants. Finally, all participants, regardless of randomization, will have postoperative indwelling urethral catheters until voiding trials are performed.

STUDY INTERVENTION:

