The primary intervention is concomitant placement of any full-length macroporous, monofilament polypropylene bottom-up Retropubic Sling (manufactured by Boston Scientific; Ethicon; Caldera; or Neomed) VERSUS Altis™ single-incision sling (Coloplast, Minneapolis, MN) during completion of native tissue vaginal repair, including colpocleisis. If an anterior or apical procedure is planned, the sling must be tensioned following completion of these steps. Prolapse procedures will be recorded but not controlled by study protocol. Participating surgeons are all extensively experienced in RP sling passage and are required to have performed at least 5 SIS procedures prior to enrolling participants in this trial. In order to minimize the risk of altering the urethrovesical angle and the likelihood of postoperative stress urinary incontinence, any anterior repair will be conducted using an incision proximal to the bladder neck level and separate from sling incisions. Allowable techniques for prolapse repair include anterior and posterior colporrhaphy (plication of fibromuscular vaginal tissue), vaginal paravaginal repair, sacrospinous ligament suspension (either of uterus or vaginal apex), uterosacral ligament suspension (either of uterus or vaginal apex, through vaginal or laparoscopic approach) levator plication or colpocleisis. Any use of allograft, xenograft, or synthetic graft material for POP repair will not be permitted.

Standardized technique of RP sling placement

Retropubic procedures will all be performed using the vaginal or “bottom-up” approach as described by the manufacturers (Ethicon; Boston Scientific; Caldera; Neomed). Subjects will be placed in Trendelenburg position, the legs lowered to lithotomy position, and the bladder completely drained. A 1.5 cm incision will be made at the mid-urethra through a separate vaginal incision with lateral dissection with Metzembbaum scissors. After placement of both trocars, cystoscopy with a 70-degree scope will be performed to assess for bladder and urethral injury. Surgeons will set the tension of the TVT slings so that a spacer can be placed between the sling and the urethra. Sling tensioning will be performed after anterior and apical prolapse is corrected. Dermabond or steri strips will be applied to the suprapubic exit incisions.

Standardized technique of SIS placement

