Site staff must not make any changes or deviate from this protocol, except to protect the life and physical well-being of a subject in an emergency. Site staff shall notify the PI and the reviewing IRB of any deviation from the investigational plan to protect the life or physical well-being of a subject in an emergency, and those deviations which affect the scientific integrity of the clinical investigation. Such notice shall be given as soon as possible, but no later than 5 working days after the emergency occurred. Local IRB/regulatory requirements will prevail if sooner than 5 working days. All deviations from the investigational plan, with the reason for the deviation and the date of occurrence, must be documented and reported to the Data Coordinating Center. Study sites may also be required to report deviations to their IRB per local guidelines and government regulations.

Data Safety Monitoring Board

A data safety monitoring board (DSMB) will be established that is made up of two independent physicians with no connection to the conduct of this clinical trial who have no relevant conflicts of interests. The PI will review the DINDO grading of any sling related post adverse events within 48 hours of reporting and will immediately report these events to the DSMB. The DSMB will receive a progress report of study recruitment, enrollment, and retention every 6 months and make a determination regarding appropriate continuation of the study.

REPORTING ADVERSE EVENTS:

Adverse events will be recorded and reported according to criteria and timeline below. Sites will also follow local regulatory standards for AE reporting.

All study-related AEs must be recorded on the AE CRF supplied by the coordinating site, entered into the site AE log, then entered into REDCap. Each AE will be sequentially numbered according to patient. For example, patient 003's first AE would be 003.01. Each site investigator will determine the relationship of the AE to the operative procedures, the relationship of the AE to the device, along with the severity of each reportable AEs. All complications will be evaluated by the sub-sites with PI ([name]) being the deciding factor for the DINDO score (See Table Below). The sub-sites will also determine if the complications are more likely to be related to the overall surgery, sling surgery or both. Complications that are deemed not related to the surgery will be excluded (For example, a MI at >3mo postop.)

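### Is it wrong to declare non-inferiority on the per-protocol set alone, with intent-to-treat as a secondary analysis?

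*Protocol*

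**What the plan says.** All the relevant rules stand in the Power Calculation section of the protocol. The decision rule is: "Non-inferiority was declared if the upper bound of the 95% confidence interval" for the difference in abnormal bladder function is under 12%. On the analysis set, "only women treated per protocol (ie: underwent the randomized sling) were considered in the primary outcome analysis"; the reason given is to avoid a lean toward finding non-inferiority. Then: "A secondary analysis of the primary outcome was performed on the intent to treat population". The sample size is derived "using a two-group large-sample normal approximation test of proportions with a one-sided 5% significance level".

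Three other sections bear on who could be excluded:

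- Randomization and Masking: "Randomization will be assigned in the operating room to minimize surgeon and participant bias", and also "While it is impossible for surgeons to be masked to the randomization".
- Study Intervention: surgeons are experienced with retropubic (RP) slings and are "required to have performed at least 5 SIS procedures prior to enrolling participants in this trial" with the single-incision sling (SIS).
- Protocol Deviations: site staff may not depart from the protocol except to protect a participant in an emergency, and "All deviations from the investigational plan, with the reason for the deviation and the date of occurrence, must be documented".

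**The concern.** A per-protocol set is defined by something that happens after randomisation. The protocol's reason for using it covers one direction of bias: women who cross over make the arms look alike, and removing them takes that dilution away. The opposite can also occur. If women allocated to the SIS do not receive it because the placement went badly, and they then do poorly, their failures leave the deciding analysis and the SIS looks better than it is. Surgeons know the allocation and may have placed as few as five of these slings, so losses confined to the SIS arm are conceivable.

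As written, a per-protocol pass with an intent-to-treat fail would still count as non-inferior. A false claim of non-inferiority for the newer device would be at stake.

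**Working it through.** **The plan's own figure.** Inputs from Power Calculation: RP cure 82%, margin 12 points, one-sided 5%, power 80%. Equal cure in the two arms is assumed, since no SIS rate is stated.

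n = (1.645 + 0.842)² × 2 × 0.82 × 0.18 / 0.12² = 126.7, so 127 per arm, as stated. Enrolling 280 with 10% loss leaves 280 × 0.9 / 2 = 126 evaluable per arm, which is used below.

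**Can the two sets disagree?** The upper bound is p_S − p_R + z × √[p_S(1 − p_S)/n_S + p_R(1 − p_R)/n_R]. Take RP 23/126 abnormal (18.25%) and three SIS women excluded. The protocol does not settle here whether its 95% interval is two-sided, so both readings are shown.

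| Reading | Per-protocol | Intent-to-treat, 2 of 3 excluded abnormal | Intent-to-treat, 1 of 3 abnormal |
|---|---|---|---|
| z = 1.96 | 24/123: 10.98% | 26/126: 12.15% | 25/126: 11.28% |
| z = 1.645 | 26/123: 11.17% | 28/126: 12.28% | 27/126: 11.43% |

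First row in full: 0.0126 + 1.96 × 0.0496 = 0.1098, against 0.0238 + 1.96 × 0.0498 = 0.1215. Disagreement is possible, but this example needs a result at the margin and two failures among three excluded women. With one failure both sets pass.

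**How often would it produce a false declaration?** The protocol gives neither an exclusion rate nor an outcome rate for excluded women, so both are assumptions. Set the true intent-to-treat rates at 18% (RP) and 30% (SIS), exactly at the margin. Let k be the fraction excluded and f their failure rate. The treated women in an affected arm then fail at (arm rate − k × f)/(1 − k). For k = 5%:

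- SIS only, f = 18%: (0.30 − 0.009)/0.95 = 30.6%; per-protocol difference 12.6 points.
- SIS only, f = 30%: 30.0%; difference 12.0 points.
- SIS only, f = 50%: (0.30 − 0.025)/0.95 = 28.9%; difference 10.9 points.
- Both arms, f = 50%: 28.9% against (0.18 − 0.025)/0.95 = 16.3%; difference 12/0.95 = 12.6 points.

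A true per-protocol difference above 12 points makes the test conservative, and one below 12 makes it liberal. Simulation (1,000,000 trials per setting, the bound above) gives these false-declaration rates for per-protocol alone, at 2% / 5% excluded:

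| Who is excluded | 95% interval, z = 1.96 | One-sided 5%, z = 1.645 |
|---|---|---|
| SIS only, f = 18% | 2.3% / 2.0% | 4.6% / 4.0% |
| SIS only, f = 30% | 2.6% / 2.6% | 5.1% / 5.2% |
| SIS only, f = 50% | 3.1% / 4.1% | 6.0% / 7.6% |
| Both arms, f = 50% | 2.3% / 2.0% | 4.6% / 4.0% |

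Intent-to-treat alone runs at about 2.6% and 5.2% in the same simulations, so only the third row shows inflation. Inflation also arises if the RP arm loses women who do unusually well: RP-only exclusion with 5% failure gives roughly 3% under the 95% interval. Every inflating case needs exclusion that is both lopsided and strongly tied to outcome.

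**What would requiring both sets do?** In the SIS-only, 50% case, false declarations fall to 2.5% (95% interval) and to between 4.9% and 5.0% (one-sided 5%). Now let treated women fail at 18% in both arms, with the same exclusions. Power falls from 69.5% to 64.5% (k = 2%) and from 69.0% to 56.5% (k = 5%) under the 95% interval. At one-sided 5% it falls from 79.7% to 75.1% and from 79.0% to 67.9%. The true intent-to-treat difference there is only k × (50 − 18) points, that is 0.6 to 1.6, so the lost declarations would have been correct. If excluded women fail at 18%, the loss is 1 to 2 points.

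**The case for a change.** The strongest case for acting is that the protocol itself fixes the deciding set, so the choice is not simply left to a later analysis plan. Its stated reason is incomplete, because exclusion after randomisation can bias in either direction. Both analyses are already planned and reasons for deviations are recorded. Requiring both to pass needs no adjustment of the significance level, and it would hold the error rate in the one scenario that inflates it.

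The statement about bias stands: per-protocol is not conservative in every circumstance. The mechanism has little support in the text. Nothing says that surgeons choose the sling once allocation is known. The deviations section forbids departures outside emergencies, and surgeons must also watch a standardised video of the SIS technique before launch. The per-protocol definition removes no one for later revision, retreatment or other deviations, so those failures stay in the deciding analysis.

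The absence of a stated rule for discordant results also stands as an observation. Such a rule, and the reporting of exclusions by arm and reason, is commonly left to a statistical analysis plan, which is not at hand.

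**Conclusion.** The concern does not hold. The protocol names one primary set, gives a reason for it and commits to analysing the same outcome by intent-to-treat, so a disagreement would be visible to any reader. No statement is wrong and no two passages conflict.

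The possible harm depends on assumptions that the document does not support: exclusions in one arm only, with outcomes far from those of treated women. Under the least favourable case examined (5% of SIS women excluded, half of them failing), the false-declaration rate is 4.1% against about 2.6% for intent-to-treat with the 95% interval, or 7.6% against about 5.2% at one-sided 5%. With symmetric exclusion, or with excluded SIS women failing at 18% or 30%, there is no inflation.

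A both-sets rule is a legitimate alternative convention, but it is a trade-off and not a correction: in the very case it targets it costs 5 to 13 points of power under the 95% interval. Evidence of substantial, lopsided non-receipt of the allocated sling would change this assessment; the protocol offers none.

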To conduct a multi-center, prospective, randomized, single-blind trial of retropubic (RP) versus single-incision sling (SIS) in women with \geq Stage II pelvic organ prolapse and objectively confirmed stress urinary incontinence who are undergoing native tissue vaginal repair.

The **primary outcome** will be **abnormal lower urinary tract function**, a composite outcome defined as the presence of any the following at 1 year post-surgery: subjective stress incontinence symptoms or retreatment for persistent / de novo stress urinary incontinence or retreatment for urinary retention. This study is a non-inferiority study design.

Hypothesis 2: SIS is associated with fewer intra-and post-operative complications up to 1 year following surgery due to fewer sling related complications including urinary tract injury; bleeding; de novo or worsening urge incontinence symptoms; urinary tract infection, mesh exposure, need for prolonged catheter drainage and reoperations than RP slings.

Specific Aim 2:

To compare intra- and post-operative sling related complications, de novo or worsening urge incontinence symptoms and need for prolonged bladder drainage up to 1 year post-operatively in women randomized to RP versus SIS sling at the time of native tissue vaginal repair.

SUBJECT SELECTION

Inclusion Criteria

1. At least 21 years of age
2. Women being considered for a native tissue vaginal repair in any vaginal compartment or colpocleisis
3. POP \geq stage II of any vaginal compartment, according to the pelvic organ prolapse quantification (POP-Q) system [31]
4. Vaginal bulge symptoms as indicated by an affirmative response to question 3 of the PFDI-SF20 with some degree of bother (answer must be somewhat, moderately, or quite a bit): Do you usually have a bulge or something falling out that you can see or feel in the vaginal area?
5. Positive standardized cough stress test on clinical examination, or on urodynamic testing
6. Understanding and acceptance of the need to return for all scheduled follow-up visits and willing to complete study questionnaires
7. Able to give informed consent

Exclusion Criteria

1. Prior surgery for stress urinary incontinence including mid-urethral sling; Burch/MMK; fascial pubovaginal sling (autologous, xenograft or allograft; urethral bulking injection)
2. Status post reconstructive pelvic surgery with transvaginal mesh kits or sacrocolpopexy with synthetic mesh for prolapse

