All surgeons will watch a standardized video regarding SIS sling placement prior to study launch. A 1.5 cm incision will be made at the level of the mid-urethra. The sling/needle assembly is advanced behind the ischiopubic rami in a transobturator trajectory toward the obturator space bilaterally. The needle is then removed by simply sliding the fixating tip back out. The other side is then completed in an identical fashion. The sling will be tensioned so that it will lie in direct apposition to the urethra but will still permit passage of an instrument between the mesh and the urethra. The adjustment thread is then cut short and the vaginal incision is closed with an absorbable suture.

Following SIS placement, **2 small superficial skin incisions will be made in the same location as the exit sites of a RP sling.** Dermabond or steri strips will be applied.

Any intra-operative adverse events will be recorded on data collection forms.

Post-operative care and procedures for voiding trials will not be standardized. Day of discharge and method of voiding (spontaneous, self-catheterization, suprapubic catheter, or indwelling foley) will be recorded.

POST-INTERVENTION ASSESSMENTS:

The primary study endpoints will be assessed at 6 weeks and 12 months after the index surgery via a clinic visit and health-related quality of life interview/completion of questionnaires. Individual site study coordinators will collect follow-up healthcare utilization data and update the medical history at 6 and 12 months. Study coordinators will complete a telephone interview at 6 months to assess for any Adverse Events.

Clinical outcomes

This trial has a composite **primary** dichotomous outcome of **abnormal lower urinary tract function** at 12 months post-operatively (YES or NO) that is defined as ANY of the following:

1. Subjectively bothersome stress incontinence symptoms at 12 months post-operatively, as measured by a positive response of > 1 to Question 17 on PFDI-20.
2. Any retreatment for stress incontinence including pelvic floor physical therapy; incontinence pessary; urethral bulking injection; repeat incontinence surgery
3. Surgical intervention for urinary retention (sling lysis or revision) at any time point post-operatively

Secondary outcome measures will assess the degree to which the study intervention influences adverse events intra- and post-operatively and will include the following:

1. Adverse events

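### Aim 2's sling-related complication comparison rests partly on site attribution with no masking described, and listed events judged unrelated can go unrecorded

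*Protocol*

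**What the plan says.** **The comparison.** Specific Aim 2 is "To compare intra- and post-operative sling related complications", together with urge symptoms and prolonged drainage, up to 1 year. Hypothesis 2 is directional: "SIS is associated with fewer intra-and post-operative complications up to 1 year following surgery due to fewer sling related complications".

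**The setting.** Under Study Intervention, the sling is placed during a native tissue prolapse repair whose type is recorded but not controlled.

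**Who attributes.** Under Reporting Adverse Events, "Each site investigator will determine the relationship of the AE to the operative procedures, the relationship of the AE to the device". The same section adds: "The sub-sites will also determine if the complications are more likely to be related to the overall surgery, sling surgery or both". The principal investigator has the final say on the Dindo grade. No such role is given for attribution, and the data safety monitoring board is given none either.

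**Masking.** Randomization and Masking says "While it is impossible for surgeons to be masked to the randomization", whereas participants are masked for the year. The operative note lists the sling neutrally under procedures but must "describe the type of sling used within the body of the operative note". No masked assessor of adverse events is described.

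**What is recorded.** An adverse event is defined as any untoward occurrence, related or not. The recording instruction, however, covers study-related events, and complications deemed unrelated to the surgery are excluded (the example is a myocardial infarction more than 3 months after surgery). The list of reportable events is limited to those determined to be related to the operative procedures or the device.

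**The outcome list.** Under Clinical outcomes, "Secondary outcome measures will assess the degree to which the study intervention influences adverse events intra- and post-operatively", and the first item is adverse events, with no restriction to sling-related ones.

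**The concern.** Randomisation protects a comparison of events by arm. It does not protect a comparison of events that someone who may know the arm has classified as due to the sling. If ambiguous events are labelled differently in the two arms, the sling-attributed rates differ even when the true event rates are equal. The shift could favour SIS if those judging share Hypothesis 2, or go against SIS if a newer device attracts more attribution.

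The recording rule is a second and separate matter. Hypothesis 2 counts UTI among the complications of interest up to 1 year. A UTI late in that year that a site judges unrelated need not be entered at all. How to tabulate events can be settled in a statistical analysis plan; an event that was never entered cannot be recovered there.

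What is at stake is part of one secondary comparison.

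**Working it through.** **1. Which events depend on the label.** Take the Hypothesis 2 events, the reportable list and the secondary outcomes in turn.

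- *Either procedure can cause it, so the label decides:* bleeding, UTI, some urinary tract injuries, retention, hematoma, some reoperations.
- *Only the sling can cause it:* trocar perforation, and mesh exposure, because "Any use of allograft, xenograft, or synthetic graft material for POP repair will not be permitted".
- *Not defined by attribution:* urge symptoms (PFDI-20 Question 16), bladder drainage beyond 6 weeks, and the primary composite.

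**2. What unequal labelling could do.** The protocol states no complication or attribution rate, so there is no figure of its own to reproduce. The only input from it is the enrolment goal of 280 (Power Calculation), giving 280/2 = 140 per arm. Everything else here is assumed.

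Let a be the true rate of ambiguous events, equal in both arms, and let s be the share called sling related. Then

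- spurious difference = a × (s_RP − s_SIS);
- test: z = (p1 − p2)/√(2p̄(1 − p̄)/140), significant if |z| > 1.96, with probabilities from exact enumeration of the two binomials.

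With s_RP = 0.5, for example, a = 0.20 and s_SIS = 0.3 give 0.20 × (0.5 − 0.3) = 0.04, that is 10% against 6%. Chance of a significant result in the direction of the bias (nominal 2.5%):

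| a | s_SIS = 0.4, favours SIS | s_SIS = 0.3, favours SIS | s_SIS = 0.6, favours RP | s_SIS = 0.7, favours RP |
|---|---|---|---|---|
| 10% | 6% | 12% | 5% | 10% |
| 20% | 8% | 22% | 8% | 17% |
| 30% | 11% | 34% | 10% | 26% |

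With equal shares the result is about 2.5% each way. With fewer ambiguous events the effect nearly vanishes: at s_SIS = 0.4, a = 3% gives 3.1% and a = 5% gives 4.1% favouring SIS. A comparison without attribution has no s in it, so its expected difference here is a − a = 0.

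**3. What dropping attribution costs.** Assume true sling complications of 20% (RP) and 10% (SIS), and independent repair complications at rate r in both arms. The any-complication rate is 1 − (1 − sling rate)(1 − r).

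| r | RP | SIS | Power |
|---|---|---|---|
| perfect attribution | 0.20 | 0.10 | 65.9% |
| 5% | 1 − 0.80 × 0.95 = 0.240 | 1 − 0.90 × 0.95 = 0.145 | 52.5% |
| 10% | 1 − 0.80 × 0.90 = 0.280 | 1 − 0.90 × 0.90 = 0.190 | 42.8% |
| 15% | 1 − 0.80 × 0.85 = 0.320 | 1 − 0.90 × 0.85 = 0.235 | 35.8% |

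The attribution-free comparison is therefore a useful companion but a poor replacement.

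**4. The recording rule.** No arithmetic applies. The definition of an adverse event includes unrelated events, while the recording instruction, the exclusion and the reportable list each require a judgement of relatedness. UTI is on that list, so a late UTI judged unrelated meets the definition but need not reach the database.

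**The case against.** The strongest reply is that the protocol already allows the safer comparison. Its secondary outcome is adverse events without restriction, secondary outcomes are analysed by intention to treat, and events attributed only to the repair are still reportable because they relate to the operative procedures. That stands for sling-or-repair ambiguity: the data for an attribution-free count should exist. But Specific Aim 2 is itself worded as a comparison of sling-related complications, so the safer count is available without being tied to the aim.

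It can also be said that every rate above is assumed, that the larger figures need 20% to 30% ambiguous events and a 50% against 30% labelling gap, and that unmasked surgeons are openly declared. All of that stands and keeps the point small.

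A reader might infer more than the text supports:

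- *That the exclusion of unrelated complications removes the ambiguous events.* It does not. An event due to the sling or the repair is related to the surgery either way; the rule reaches only events judged due to neither.
- *That leaving open how events labelled as both are counted is an error.* That is detail a statistical analysis plan commonly settles, and that plan is not at hand.
- *That the relatedness scales are faulty because the procedure and device versions are worded alike.* They address different objects, and the separate three-way question already allows for shared causes.
- *That the operating surgeon attributes the events.* The protocol says sub-sites and site investigators, and describes no masking; it goes no further.

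**Conclusion.** The point holds as a minor one. For events that either procedure can cause, part of the Aim 2 comparison depends on a site judgement with no masking described, and the recording rules can lose listed events judged unrelated. Both are conduct rules fixed in the protocol.

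It would be wrong to conclude that the comparison is biased, or biased towards SIS: the protocol gives no rates from which size or direction could be derived. On the assumptions shown, the chance of a spurious result in the direction of the bias runs from barely above the nominal 2.5% to about a third, depending on how common ambiguous events are and how unequally they are labelled. How many listed events the recording rule would lose cannot be estimated from the document; since its own example is a late myocardial infarction, the number may be small.

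The primary outcome, mesh exposure, trocar perforation, Question 16 urge symptoms and drainage beyond 6 weeks are not affected.

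**What to change.** 1. **Reporting Adverse Events:** record the listed event types in both arms regardless of judged relatedness. Keep the relatedness judgement as a data field instead of a condition for recording. The exclusion can remain for events that are not on the list, such as its own example.
2. **Specific Aim 2:** report the event types named in Hypothesis 2 by randomised arm without attribution, with confidence intervals, beside the sling-attributed comparison.

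The cost is a few more adverse event forms and one more table. The attribution-free comparison is diluted by repair complications (power of about 52% down to 36%, against 66% with perfect attribution, on the assumed rates), so the sling-attributed comparison should stay. The first change helps only for events still to be recorded; the second can be made at any time before analysis. Neither change removes unmasked detection and reporting, which should be acknowledged when the results are interpreted.
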